##### **11.5.1 Product Complaint Information Needed from the Investigational Center**

In the event that the Product Complaint Form cannot be completed, the investigator (or qualified designee) will obtain the following information, as available:

- investigational center number and investigator (or qualified designee) name
- name, phone number, and address of the source of the complaint
- clinical protocol number
- patient identifier (patient study number) and corresponding visit numbers, if applicable
- product name and strength for open-label studies
- patient number, bottle, and kit numbers (if applicable) for double-blind or open-label studies
- product available for return Yes/No
- product was taken or used according to protocol Yes/No
- description or nature of complaint
- associated SAE Yes/No
- clinical supplies unblinded (for blinded studies) Yes/No
- date and name of person receiving the complaint

Note: Reporting a complaint must not be delayed because not all the required information can be immediately obtained. Known information must be immediately reported. The

sponsor will collaborate with the investigator (or qualified designee) to obtain any outstanding information.

#### **11.5.2 Handling the IMP at the Investigational Center**

The investigator (or qualified designee) is responsible for retaining the product in question in a location separate from the investigator's (or qualified designee's) clinical study supplies. The Sponsor may request that the investigator (or qualified designee) return the product for further evaluation and/or analysis. If this is necessary, the mobile nurse or designee will provide the information needed for returning the IMP.

If it is determined that all of the IMP must be returned, the Sponsor will provide the information needed to handle the return by the mobile nurse.

#### **11.5.3 Adverse Events or Serious Adverse Events Associated with a Product Complaint**

If there is an AE or SAE associated with a product complaint, the protocol should be followed (see Section [11.5.4](#)).

#### **11.5.4 Documenting a Product Complaint**

The investigator (or qualified designee) will record a description of the product complaint in the source documentation as well as any actions taken to resolve the complaint and to preserve the safety of the patient. Once the complaint has been investigated by the Sponsor and the investigator (or qualified designee), if necessary, an event closure letter may be sent to the investigational center where the complaint originated or to all investigational centers using the product.

## **DSM-IV TR CRITERIA FOR SUBSTANCE ABUSE**

### **DIAGNOSIS – CRITERIA FOR SUBSTANCE ABUSE**

A. A maladaptive pattern of substance use leading to clinically significant impairment or distress, as manifested by 1 (or more) of the following, occurring within a 12-month period:

- (1) recurrent substance use resulting in a failure to fulfill major role obligations at work, school, or home (e.g. repeated absences or poor work performance related to substance use; substance-related absences, suspensions, or expulsions from school; neglect of children or household)
- (2) recurrent substance use in situations in which it is physically hazardous (e.g. driving an automobile or operating a machine when impaired by substance use)
- (3) recurrent substance-related legal problems (e.g. arrests for substance-related disorderly conduct)
- (4) continued substance use despite having persistent or recurrent social or interpersonal problems caused or exacerbated by the effects of the substance (e.g. arguments with spouse about consequences of intoxication, physical fights)

The symptoms have never met the criteria for Substance Dependence for this class of substance

**LIST OF ABBREVIATIONS AND DEFINITIONS OF TERMS**

Abbreviation	Term
AE	adverse event
BMI	body mass index
CAG	Cytosine-Adenosine-Guanine
CRF	case report form
C-SSRS	Columbia-Suicide Severity Rating Scale
ECG	electrocardiogram
FA	Functional Assessment
IS	Independence Scale
ITT	intent-to-treat
MedDRA	Medical Dictionary for Regulatory Activities
PBA-s	Problem-Behaviors Assessment-Short Form
PT	preferred term
R&D	Research and Development
SAP	statistical analysis plan
SD	Standard Deviation
SE	Standard Error
SOC	system organ class
SOP	standard operating procedure
TFC	Total Functional Capacity
TMS	Total Motor Score
UHDRS	Unified Huntington's Disease Rating Scale
WHO	World Health Organization

## INTRODUCTION

This Statistical Analysis Plan (SAP) describes the planned analysis and reporting for Teva Branded Pharmaceutical Products R&D, Inc. study ACR16C015, (A multi-center, open-label extension study of pridopidine (ACR16) in the symptomatic treatment of Huntington's Disease (Open-HART)), and was written in accordance with SOP GBP\_RD\_702 (Statistical Analysis Plan).

The reader of this SAP is encouraged to read the study protocol for details on the conduct of this study, the operational aspects of clinical assessments, and the timing for completing the participation of a patient in this study.

The SAP is intended to be in agreement with the protocol, especially with regards to the primary and all secondary endpoints and their respective analyses. However, the SAP may contain more details regarding these particular points of interest, or other types of analyses (e.g. other endpoints). When differences exist in descriptions or explanations provided in the study protocol and this SAP, the SAP prevails; the differences will be explained in the Clinical Study Report.

## **1. STUDY OBJECTIVES**

The objective is to assess the long-term safety of pridopidine and to analyze treatment effects during long-term, open-label treatment.

The primary objective of this study is to evaluate the long-term safety of pridopidine treatment and to collect information on Unified Huntington's Disease Rating Scale (UHDRS) development during long-term, open-label treatment.

## 2. STUDY DESIGN

### 2.1. General Design

Note: the SAP is based on Protocol Am 04 (dated 25 August 2016), and that Protocol Am 05 was issued (on 29 June 2017) for study virtualization but was not implemented.

This is a multi-center open-label study of pridopidine 45mg bid for patients who completed the ACR16C009 (HART) or TV7820-CNS-20002 (PRIDE-HD) studies.

At the **Baseline Visit** the following tests will be performed and documented: review and completion of informed consent; review of inclusion and exclusion criteria; pregnancy test (for females of childbearing potential); review of (baseline) adverse events (AEs), concomitant medication and medical history. All patients will be assessed for suicidality using the Columbia-Suicide Severity Rating Scale (C-SSRS). Evaluation for Research Study Consent and blood draw (calcium, magnesium, potassium, and creatinine for creatinine clearance calculation) will be performed for patients from the PRIDE-HD study.

The following assessments will be performed: physical examination including vital signs (heart rate and blood pressure) and weight; review of concomitant medication; (including inquiry about changes in use of benzodiazepines and antidepressants); inquiry about changes in use of alcohol and illicit drugs; UHDRS (including motor assessment, cognitive assessment, behavioral assessment, functional capacity, independence scale, functional assessment); 12-lead electrocardiogram (ECG) (single).

Trial medication will be dispensed and an appointment made for the next visit.

At **Telephone Visit 1 (T1, Week 1)** an evaluation for research study consent will be conducted, any AEs will be collected and reported, compliance will be confirmed, concomitant medication reviewed (including inquiry about changes in use of benzodiazepines and antidepressants); inquiry about changes in use of alcohol and illicit drugs, C-SSRS, abbreviated Problem-Behaviors Assessment-Short Form (PBA-s), and an appointment for next contact will be made. Evaluation for Research Study Consent will be performed for patients from the PRIDE-HD study.

At **Visit 1 (1 Month)** the following will be documented: an evaluation for research study consent, review of concomitant medications (including inquiry about changes in use of benzodiazepines and antidepressants); inquiry about changes in use of alcohol and illicit drugs, AEs, C-SSRS, PBA-s, vital signs and drug compliance. Evaluation for Research Study Consent, ECG and blood draw (calcium, magnesium, potassium, and creatinine for creatinine clearance calculation) will be performed for patients from the PRIDE-HD study.

Subsequently, the patient will be contacted every 3 months as per below:

At **Telephone or in-person Visits [Safety Visit (SV)] (eg after 3, 9, 15 months etc.)** the following will be documented: an evaluation for research study consent, review of concomitant medication (including inquiry about changes in use of benzodiazepines and antidepressants); inquiry about changes in use of alcohol and illicit drugs, C-SSRS and PBA-s assessment, review of AEs, and assessment of compliance with trial medication. A 12-lead ECG will be obtained, vital signs will be assessed and calcium, magnesium and potassium level and creatinine for

creatinine clearance calculation will be drawn [hypokalemia is defined as a potassium level less than 3.5 mEq/L]. If less than 3.5 mEq/L, patient's study drug will be suspended until normal (greater than or equal to 3.5mEq/L). Participants can choose to have the assessments of vital signs, ECG and blood draw for calcium, magnesium, potassium, and creatinine for creatinine clearance calculation performed by their GP and/or local cardiologist or schedule a visit with site but the site must have a telephone contact with the participant to review concomitant medication, AEs and assess compliance with trial medication.

At **Telephone contacts [C] (eg once a month between on-site visits)** the following will be documented: an evaluation for research study consent, review of concomitant medication (including inquiry about changes in use of benzodiazepines and antidepressants); inquiry about changes in use of alcohol and illicit drugs, review of adverse events, C-SSRS and an abbreviated PBA-s assessment.

At **Clinic Visits (eg 6, 12, 18 months etc.)** the following tests will be performed and documented: an evaluation for research study consent, brief physical examination including vital signs and weight, calcium, magnesium, and potassium levels and creatinine for creatinine clearance calculation will be drawn [hypokalemia is defined as a potassium level less than 3.5 mEq/L]. If less than 3.5 mEq/L, patient's study drug will be suspended until normal (greater than or equal to 3.5mEq/L), review of concomitant medication (including inquiry about changes in use of benzodiazepines and antidepressants); inquiry about changes in use of alcohol and illicit drugs, review of AEs, C-SSRS, PBA-s, 12-lead ECG and assessment of compliance with trial medication. On a yearly basis, UHDRS (including motor assessment, cognitive assessment, behavioral assessment, functional capacity, independence scale, functional Assessment) and a pregnancy test (for females of childbearing potential) should be done. The PBA-s will be collected at all safety and clinic visits except on those at which the UHDRS is performed.

#### **Withdrawal from treatment**

If the patient wishes to stop the drug, or is judged by the investigator to not be suitable for continued therapy, or the study is discontinued, a clinic visit ("withdrawal visit", end of study drug visit) should be performed and the patient withdrawn from the study. A (telephone) follow-up visit (30 d TC F/U) to collect and report AEs (as well as inquiry about changes in use of benzodiazepines and antidepressants, and inquiry about changes in use of alcohol and illicit drugs), C-SSRS and an abbreviated PBA-s assessment should take place one month after the actual discontinuation of study drug took place.

Patients who discontinue study medication due to safety or tolerability reasons may continue in the study off drug and perform the scheduled visits and assessments.

#### **Unscheduled Visit(s)**

If a patient has tolerability problems, or has to de-escalate the investigational treatment, the investigator can decide to call the patient to an unscheduled study visit at the study center. Where a patient attends an Unscheduled Visit between the scheduled visits they should be instructed to attend their next visit according to the study schedule as planned.

Schedule of assessments are outlined in Table 1.2 of the protocol.

## **2.2. Efficacy Measures**

- Unified Huntington's Disease Rating Scale – Total Motor Score (UHDRS-TMS)
- Unified Huntington's Disease Rating Scale – Total Functional Capacity (UHDRS-TFC)
- Unified Huntington's Disease Rating Scale – Functional Assessment (UHDRS-FA)
- Unified Huntington's Disease Rating Scale – Independence Scale (UHDRS-IS)
- UHDRS Behavioral Assessment
- UHDRS Cognitive Assessment
- PBA-s (also part of safety measures)

## **2.3. Safety Measures**

- AEs
- Vital signs assessments
- ECG findings
- Concomitant medication usage.
- Physical examination findings
- Suicidality (C-SSRS and PBA-s)

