### **7.7.1 Cessation of Treatment**

A patient will be classified as having ceased treatment when he or she discontinues IMP, prior to the completion of the prescribed course for any of the following reasons:

- AE
- Death
- Lost to follow up
- Patient withdrew consent
- Major protocol violation
- Pregnancy

- 
- Treatment is no longer appropriate
  - Termination of study

If hypokalemia is observed, dosing will be interrupted and should not be started again until normal electrolyte values are confirmed by re-draw and maintained for 7 days. Patients needing more than 14 days to reach stable potassium levels, without IMP, should be withdrawn from the IMP. The patient will be asked to continue in the study and follow the visit schedule as outlined in the protocol.

In instances where there is an increase in QT/QTcF of >500ms or 60ms over VTV, a second ECG should be repeated after 10 minutes rest to confirm the finding. Where confirmed, this should be reported and documented on the eCRF as an AE.

Patients with a QTcF interval of >500 ms, or with an increase in the average QTcF value >60 ms from the VTV, should be discontinued from the study. A follow-up ECG should be done in 4 weeks.

Patients should also be discontinued if:

- they experience a seizure or convulsions (regardless of the relationship to treatment);
- their body weight decreases to <50 kg (may be discontinued based on investigator (or qualified designee) or Sponsor discretion);
- and/or if creatinine clearance decreases to <60 mL/min (calculated using the Cockcroft-Gault equation). It is allowed to repeat the test once, if clinically appropriate.
- they experience an AE/SAE of suicide ideation or attempt; or
- they have a C-SSRS suicidal ideation score  $\geq 3$  (i.e. who answer "Yes" to questions 3, 4, and 5 in the scale suicidal ideation section); or
- they have a C-SSRS report of suicidal act; or
- they have an abbreviated PBA-s suicidal ideation item score  $\geq 3$  (i.e. 3, 4).

Patients who discontinue treatment with IMP due to safety or tolerability reasons may continue in the study off IMP and perform the scheduled visits and assessments.

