### **8.9.3 Other Safety Parameters**

Changes in other safety parameters (e.g. QTcF, vital signs, and body weight) will be presented by yearly intervals overall.

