## **2.5. Sample Size and Power Considerations**

As this is an open-label extension study, no sample size calculations have been performed. Patients who completed the HART or the PRIDE-HD study and met patient exclusion/inclusion criteria will be enrolled.

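### The SAP plans no summary of the potassium, calcium, magnesium or creatinine-clearance results it schedules, so the primary long-term safety report would be incomplete

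*SAP*

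**What the plan says.** SAP 1 states the purpose: "The primary objective of this study is to evaluate the long-term safety of pridopidine treatment", together with collecting UHDRS data.

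SAP 2.1 sets out the laboratory schedule. At baseline, and again at Visit 1 (Month 1), "blood draw (calcium, magnesium, potassium, and creatinine for creatinine clearance calculation) will be performed for patients from the PRIDE-HD study". At the safety visits (months 3, 9, 15 and so on) the same four tests are taken along with ECG and vital signs. At the clinic visits (months 6, 12, 18 and so on) "calcium, magnesium, and potassium levels and creatinine for creatinine clearance calculation will be drawn". At both kinds of visit, potassium below 3.5 mEq/L suspends study drug until it is normal.

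SAP 2.3 lists six safety measures: AEs, vital signs, ECG, concomitant medication, physical examination and, last, "Suicidality (C-SSRS and PBA-s". SAP 7.2 to 7.8 then cover exposure, AEs, vital signs, ECG, physical examination, concomitant medication and C-SSRS.

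Protocol 8.9.1 calls for the number of patients with a dosage reduction and with a suspension of drug. Protocol 8.9.3 adds: "Changes in other safety parameters (e.g. QTcF, vital signs, and body weight) will be presented by yearly intervals overall".

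**The concern.** The plan collects four laboratory parameters over years of treatment and gives no instruction to summarise any of them. Two carry dosing consequences. Potassium can suspend the drug or lead to its withdrawal. Creatinine clearance can lead to a reduced dose frequency or to stopping. A safety report built to this SAP would give QTcF by visit and by threshold (SAP 7.5) and vital signs against stated criteria (SAP 7.4), but nothing comparable for these tests.

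A reader of the final report could not see how potassium or renal function moved over time, or how many patients crossed a level at which the plan itself intervenes. In an uncontrolled extension whose safety analysis is purely descriptive, such tables are the main product.

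**Working it through.** No arithmetic applies and the plan gives no figure to reproduce: "As this is an open-label extension study, no sample size calculations have been performed". The check compares what is collected with what is summarised.

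| Parameter | Drawn (SAP 2.1) | Dosing rule | Summary in SAP 5, 6 or 7 |
|---|---|---|---|
| Potassium | Yes | Suspension below 3.5 mEq/L (SAP 2.1; protocol 6.3.2); withdrawal from drug if more than 14 days are needed to stabilise (protocol 6.3.2, 7.7.1) | None |
| Creatinine clearance | Yes, from creatinine | Reduction or stopping (protocol 5.3.1, 6.3.2, 7.7.1) | None |
| Calcium | Yes | No threshold stated | None |
| Magnesium | Yes | No threshold stated | None |

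Coverage is 0 of 4 parameters, and 0 of the 2 with dosing rules. The SAP table of contents has no laboratory section either, so this is not a page lost in extraction.

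Next, could the information reach the report by another route?

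1. **AE tables.** Protocol 6.3.2 and 7.1.1 require clinically significant laboratory abnormalities to be recorded as AEs, and the AE definition extends to the reasons for unplanned changes of drug or dose. SAP 7.3 tabulates AEs by system organ class and preferred term, with exposure-adjusted rates. This route is real but partial. It gives no values, no changes from baseline, and no count of crossings that nobody recorded as an AE.
2. **Dose changes.** SAP 7.2 does not include the counts of reductions and suspensions in protocol 8.9.1. Its exposure formula (last day minus first day plus 1) runs straight through a suspension. SAP 7.3 has a table for AEs leading to withdrawal from the study, but none for AEs leading to suspension or reduction. SAP 9 nevertheless declares no changes from the protocol analyses.
3. **Disposition.** SAP 5.2 summarises reasons for withdrawing from treatment. That covers permanent stops only.
4. **Listings.** SAP 8 mentions listings in general and specifies none for laboratory data.

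Last, which thresholds can be used? Potassium at 3.5 mEq/L stands in the SAP itself. For creatinine clearance, the supplied protocol disagrees with itself:

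- Section 5.3.1 makes a once-daily reduction mandatory between 40 and 60 mL/min.
- Section 6.3.2 allows the lower dosage in that range at the investigator's discretion, and discontinues below 40.
- Section 7.7.1 lists among its discontinuation criteria "and/or if creatinine clearance decreases to <60 mL/min (calculated using the Cockcroft-Gault equation").

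The supplied protocol is also Amendment 05, whereas SAP 2.1 says that the SAP rests on Amendment 04 and that Amendment 05 was not implemented. These sections must be reconciled before any clearance threshold is fixed for a table.

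**The case against.** The strongest reply is that laboratory events with consequences do have a route into the report. On a plain reading of protocol 7.1.1, a potassium result that suspends drug is the reason for an unplanned change and hence an AE, with the action taken recorded (protocol 7.2.2.4) and the event counted under SAP 7.3. This stands. A reader might infer that the report would be silent on hypokalaemia and renal decline; the documents do not support that. What is missing is the laboratory data themselves and any count made directly from them.

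A reader might also infer that the SAP overrides a protocol instruction on laboratory data, because the SAP prevails where the two differ. It does not: protocol 8.9.3 does not name laboratory tests, though its examples leave room for them, and SAP 2.3 does not say that its list is exhaustive. The laboratory gap is shared by both documents.

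An analyst could also fill part of the gap from the general rules on descriptive statistics (SAP 4.1) and visit assignment (SAP 4.5). That is true of by-visit summaries. It leaves open whether they are produced at all and which thresholds count. Where a scheduled and an unscheduled result fall on the same visit, SAP 4.5 keeps the scheduled one, so an unscheduled low potassium could drop out of a by-visit table.

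**Conclusion.** The point holds as an incomplete safety analysis that should be corrected before database lock. None of the four scheduled laboratory parameters has a planned summary. The counts of dose reductions and suspensions, which would show the consequences of the laboratory rules, are missing from the SAP as well.

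The size cannot be put in patients. It is tempting to use the 47 patients in the protocol synopsis to bound an event rate, but that number belongs to Amendment 05. The SAP safety set is every patient dosed, and its size is not given. It is equally tempting to multiply the 3-monthly schedule over six years, but the schedules under earlier protocol versions are not available.

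The conclusion rests on the SAP alone for the draws, the potassium rule and the missing summaries. The creatinine-clearance rules and the wording of protocol 8.9.1 are read from Amendment 05 and are assumed, not shown, to match Amendment 04 in substance.

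**What to change.** Add laboratory data to SAP 2.3 and a laboratory section to SAP 7 containing:

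- (a) descriptive values by visit for potassium, calcium, magnesium and creatinine clearance, with change from baseline where a baseline draw exists (SAP 2.1 plans one for PRIDE-HD patients);
- (b) the number and percentage of patients with any post-baseline potassium below 3.5 mEq/L, counting scheduled and unscheduled draws, as SAP 7.4 already does for vital signs;
- (c) the same for creatinine clearance at the protocol's thresholds, once protocol 5.3.1, 6.3.2 and 7.7.1 have been reconciled with each other and with Amendment 04;
- (d) the counts of patients with dosage reduction or suspension from protocol 8.9.1.

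The cost is one SAP paragraph and one or two descriptive tables, with no inference and no new data collection. One point to confirm first: SAP 2.1 lets patients have these draws done by their GP or local cardiologist, so check that those results are in the study database.
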